## **9 CONTENT OF REPORTS**

All analyses described in this SAP will be included in the Clinical Study Report(s) except where otherwise noted. Refer to the Data Presentation Plan for mock-ups of all tables and listings.

## 10 DOCUMENT HISTORY

**Table 10-1: Document History**

Version Number	Author(s)	Description
1.0		Original publication
2.0		
23NOV2020:
 
 
1. Section 2.4.1 - added details of protocol amendment 2 (Protocol revision 3).
 
2. Added note to Tables 4.1.1.1-1 and 4.1.2.1-1 that subjects with assessments with measurable disease per Investigator but no measurable disease per BICR (but who were evaluated per BICR) will be included in the analysis.
 
3. Section 4.1.3 and 4.1.4 - added notes that BOR, time to response, and duration of response per investigator will be summarized in the same manner as per BICR.
 
4. Section 7.2.1 - added relevant protocol deviation of baseline imaging performed outside required window per RECIST 1.1 and per protocol (beyond 28 days + 2 week window).
 
5. Section 7.3.2: removed time from CNS metastasis to randomization as date is not collected, but added in history of brain metastasis. Added details on the AJCC and Baseline Metastasis Stage display and programming. 50% PD-L1 cutoff was replaced with the 10% cutoff. Updated race to be as collected.
 
6. Section 6.3 - added in Phase 2 and Phase 3 populations and definitions.
 
7. Section 7.1.1.2 - updated Other Events of Special Interest which combined myositis/rhabdomyolysis together and changed aseptic meningitis to other meningitis
 
8. Section 7.3.2 - updated age, race, and region categories; added details about AJCC Stage v8 at study entry and • Baseline Metastasis Stage; removed time from CNS metastasis to randomization as we did not collect date; specified to use CRF disease history page to report brain metastasis; changed PD-L1 50% cutoff to 10% cutoff; added display PD-L1 Expression x LAG3 Status. Added in additional summaries of the demography and baseline characteristics tables for the Phase 2 and Phase 3 populations to examine consistency for all randomized participants.
 
9. Tables 7.4.1-1 - updated the duration formula to be used: last dose - first dose +1 (instead of +28)
 
10. Section 7.5.3 - updated or added details for categories of the subgroups for efficacy: age, region, m-stage, baseline metastasis stage, tumor burden at baseline per BICR (quartiles), histology. Specified the source for the data.
 
11. Sections 7.5.2 and 7.5.4 - During the course of this study a global pandemic occurred known as COVID-19. Sensitivity analyses of PFS and OS were specified due to COVID-19. These will only be performed if there are more than 10% of all PFS/OS events due to COVID-19. The hazard ratio associated with treatment will be presented along with the associated two-sided 95% CIs.
 
12. Section 7.6.1.2 - added region categories and lower bound for age category (of age 12).
 
13. Section 7.6.23 - added in analysis of ECGs
 
14. Section 7.7.1 removed plots of concentration by dose/
 
15. Section 7.8.5.1 - removed the 10% cutoff analysis for LAG3, and detailed PD-L1 to use 1, 5, and 10% cutoffs.
 
16. Section 7.9.2 - added in separate analysis of FACT-M GP5 item.
 
17. Sections 4.3.2.1, 6.2.1, 7.2.1, and 7.3.2: Added details regarding any subject who had a PD-L1 value originally scored at CMBP will have a re-score. If PD-L1 was rescored, it will be used as the primary value for analyses/stratification.
 


**Table 10-1: Document History**

Version Number	Author(s)	Description
		
The PD-L1 re-score will not be used to determine relevant protocol deviations/ineligibility, as it was scored posthoc. Also, if the re-scored value is evaluated as non-quantifiable, these will be categorized with PD-L1 negatives, unless greater than 5% of all randomized subjects are non-quantifiable, in which case there will be a 3rd category for PD-L1 stratification categories. Added in non-quantifiable whenever presenting/analyzing PD-L1 because of the rescored values. Also added in details about m-stage at IRT stratification did not accurately capture LDH value so the RAVE database will be used for the m-stage stratification value/ category.
 
18. Changed OS to the first secondary endpoint in the hierarchical testing strategy. Order is PFS, OS, ORR
 
19. Added interim analyses of OS at the time of positive PFS FA (OS IA1 at ~70% and OS IA2 at ~90% of events.
 
20. Added GP5 single item endpoint and objective (Table 3-1 and Sections 4.3.4.2 and 7.9.2)
 
21. Added TFI as an endpoint and objective (Table 3-1 and Sections 4.1.6, 7.5.10)
 
22. Section 7.1.1 - removed sentence on dose reduction.

2.1	[REDACTED]	
03MAR2021
 
 
1. Clarified in Section 7.5 what to do in the case of non-convergence due to small number of events in one of the 16 strata or if there are <10 subjects in a strata in the efficacy model.
 
2. Corrected Table 5-2.1-2, which mistakenly showed the (one-sided) cumulative alpha spent instead of the nominal p-value boundaries in the examples used to illustrate the Lan-Demets /O'Brien-Fleming spending function used for interim OS analyses.
 
3. Section 7.9 patient-reported outcome analyses modified to use All Randomized Subjects
 

3.0	[REDACTED]	
04AUG2021 update to SAP:
 
Section 5.2.1 was updated with information that the primary endpoint analysis was tested on 09MAR2021 and it was statistically significant. The first interim analysis of OS (OS IA1) was performed at the same time by the DMC and it was not statistically significant. As pre-specified, the significant results for the primary endpoint led to unblinding at the subject level and the reporting of PFS and all safety data. Also as pre-specified, OS and ORR were not analyzed, nor summarized by treatment arm. The positive results of the PFS analysis led to submission of the data to health authorities, with a filing on 04AUG2021. The current update to the SAP is the decision has been made to unblind response data at the time of the second interim OS analysis (OS IA2), anticipated for OCT2021. ORR will be unblinded and reported descriptively until (and if) OS is statistically significant and then it will be tested according to the hierarchy.

4.0	[REDACTED]	
12OCT2021 update to SAP:
 
Section 5.2.1 was updated to include the following: In the event that the database has at least 290 deaths before the second interim analysis is performed (i.e., deaths accumulate more quickly than anticipated), the second interim analysis will no longer be performed. Instead, the analysis will automatically become the final OS analysis and all deaths in the database will be used in the analysis. If this occurs, BMS, and not the DMC, will analyze the OS data and be unblinded to OS results. Table 5.2.1-3 gives details on the alpha and critical hazard ratio if no second interim analysis is performed and there are 300 deaths at the time of lock.

**Table 10-1: Document History**

Version Number	Author(s)	Description
5.0		However, this will be calculated based on the actual data in the database at the time of lock.
	[REDACTED]	The update in section 5.2.1 was revised to be more clear that the specification to remove the second interim OS analysis and go straight to the final OS analysis was made with full knowledge of how many deaths were currently in the database, but with no knowledge of the OS analysis by treatment arm.

## **APPENDIX 1 TIME TO ONSET AND TIME TO RESOLUTION DEFINITION AND CONVENTIONS FOR SELECT ADVERSE EVENTS, IMMUNE MEDIATED ADVERSE EVENTS AND EVENTS OF SPECIAL INTEREST**

### **Time-to onset definition**

Time-to onset of AE (any grade) for a specific category is defined as the time between the day of the first dose of study treatment and the onset date of the earliest AE (of any grade) in this category.

The time-to onset of AE (grade 3-5) for a specific category is defined similarly with an onset date corresponding to a grade 3-5 AE.

Time-to onset of drug-related AE (any grade or grade 3-5) for a specific category is defined similarly but restricted to drug-related AE.

Time-to onset for a specific subcategory is defined similarly but restricted to event of this subcategory.

### **Time-to resolution definition**

In order to derive the time-to resolution, overlapping or contiguous AEs within a specific category or subcategory will be collapsed into what will be termed “clustered” AEs. For example, if a subject (without pre-treatment AE) experienced an AE from 1st to 5th January, another AE (with different PT but within same category) from 6th to 11th January and same AE from 10th to 12th January, these will be collapsed into one clustered AE from 1st to 12th January. [Table 1](#) is summarizing key derivation steps for each type of clustered AEs.

Time-to resolution of AE (any grade) for a specific category is defined as the longest time from onset to complete resolution or improvement to the grade at baseline among all clustered AEs in this category experienced by the subject. Events which worsened into grade 5 events (death) or have a resolution date equal to the date of death are considered unresolved. If a clustered AE is considered as unresolved, the resolution date will be censored to the last known alive date. Improvement to the grade at baseline implies that all different events in the clustered adverse event should at least have improved to the corresponding (i.e., with same preferred term) baseline grade. This measure is defined only for subjects who experienced at least one AE in the specific category.

The time-to resolution of AE (grade 3-5) for a specific category is defined similarly with an onset date corresponding to a grade 3-5 AE.

Time-to resolution of drug-related AE (any grade or grade 3-5) for a specific category is defined similarly but restricted to drug-related AE.

The time-to resolution of AE (any grade or grade 3-5, drug-related or all) where immune modulating medication was initiated is defined similarly. For data presentation not restricted to IMAE, the additional condition that the subject started an immune modulating medication during the longest AE resolution period will be applied.

Time-to resolution for a specific subcategory is defined similarly but restricted to event of this subcategory.

**Table 1: Derivation of clustered AE**

Type of clustered AE	Derivation
Any grade	Collapse any on-treatment AE from the same category
Drug-related of any grade	Collapse any on-treatment drug-related AE from the same category
Grade 3-5 category.	Collapse any on-treatment AE from the same Resolution will be based on the onset date of the earliest grade 3- 5 records (if no grade 3-5 record, clustered AE is excluded)
Drug-related of Grade 3-5 Collapse any on-treatment drug-related AE from the same category	Resolution will be based on the onset date of the earliest grade 3- 5 record (if no Grade 3-5 record, clustered AE is excluded)

The algorithm for collapsing adverse event records is using the following conventions:

For each subject and specified category, the corresponding adverse event records will be collapsed when:

- 1) Multiple adverse event records have the same onset date.
- 2) The onset date of an event record is either the same day or 1 day later than the resolution date of a preceding event record (contiguous events).

The onset date of an event record is after the onset date and prior to or on the resolution date of a preceding event record (overlapping events).

## **APPENDIX 2 MISSING AND PARTIAL RADIOTHERAPY AND SURGERY DATES IMPUTATION ALGORITHMS**

### **Procedures – Imputation Rules.**

If reported procedure start date is a full valid date then set start date equal to the date part of procedure start date.

In case of partial date use imputation rules described below:

- If only day is missing then
  - If month and year of procedure match month and year of first dose date then impute as date of first dose;
  - If month and year of procedure don't match month and year of first dose date then impute as first day of that month and year.
- If both day and month are missing, then impute as maximum between 01JAN of the year and date of the first dose;
- If date is completely missing or invalid then leave missing.

Note: Imputation is not applicable to data where start date is not collected (for example "PRIOR RADIOTHERAPY" CRF). Set start date to missing in this case.

If reported end date is a full valid date then set end date equal to the date part of the reported end date.

In case of partial date use imputation rules described below:

- If reported end date is partial then set end date equal to the last possible reported end date based on the partial entered reported end date.
- If reported end date is missing, continuing, unknown or invalid then set end date equal to the most recent database extraction date.

If end date was imputed then compare end date to the death date or last known alive date if subject is not dead. If posterior then end date should be imputed to death date (or last known alive date if subject not dead).

Note: Imputation of partial dates only applies to data entered on "RADIOTHERAPY" CRF page. For other CRF pages in case of partial dates set end date to missing.

### **Surgeries – Imputation Rules.**

If reported surgery date is a full valid date then set start date equal to the date part of surgery date. In case of partial date, use one of the two imputation rules described below:

- A. For data collected on "PRIOR SURGERY RELATED TO CANCER" CRF page:
- If only day is missing then impute as the first day of the month;

- If both day and month are missing then then impute as 01JAN of the year;
  - If date is completely missing or invalid then leave missing.
- B. For data collected on other CRF pages (deemed to be on-treatment/subsequent surgeries):
- If only day is missing then
    - If month and year of surgery match month and year of first dose date then impute the missing date as the date of first dose;
    - If month and year of surgery don't match month and year of first dose date then impute as first day of that month and year;
  - If both day and month are missing then impute as maximum between 01JAN of the year and date of the first dose;
  - If date is completely missing or invalid then leave missing.

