7.7.2.1 Palliative Therapy

Palliative (limited-field) radiation therapy and palliative surgical resection are permitted if the following criteria are met:

- The participant is considered to have progressed at the time of palliative therapy and meets criteria to continue with treatment beyond progression (Section 8.1.2.2).
- The case is discussed with the BMS Medical Monitor/designee. Palliative therapy must be clearly documented as such in the study record.

Participants should not receive study treatment during radiation as the potential for overlapping toxicities with radiotherapy and BMS-986213 or with radiotherapy and nivolumab is currently not known. Anecdotal data suggest that radiotherapy administered to participants while receiving nivolumab therapy is tolerable. However, because concurrent radiotherapy and immunotherapies in cancer have not been formally evaluated, in cases where palliative radiotherapy is required for a tumor lesion, then all study treatments should be withheld for at least 1 week before, during, and 1 week after radiation. Participants should be closely monitored for any potential toxicity during and after receiving radiotherapy, and AEs related to radiotherapy should resolve to Grade 1 prior to resuming study treatment.

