**Figure 4.1.1.1-1: PFS Primary Definition**

**Table 4.1.1.1-1: Censoring Scheme used in Primary Definition of PFS**

Situation	Date of Progression or Censoring	Outcome
No baseline tumor assessments*	Date of randomization	Censored
No on study tumor assessments and no death*	Date of randomization	Censored
Subsequent anti-cancer therapy started without death or progression per RECIST v1.1 reported prior or on the same day	Date of last evaluable tumor assessment prior to or on the date of initiation of the subsequent anti-cancer therapy	Censored
Documented progression per RECIST v1.1 and no new anti-cancer started before	Date of the first documented progression per RECIST v1.1 (excludes clinical progression)	Progressed
No progression and no death, and no new anti-cancer therapy started	Date of last evaluable tumor assessment	Censored
Death without progression per RECIST v1.1 and no new anti-cancer started before	Date of death	Progressed

\* Tumor assessments and death if any, occurring after start of subsequent anti-cancer therapy are not considered. Note: subjects with measurable disease per Investigator but no measurable disease per BICR will be included in the analysis.

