#### **4.1.3 Objective Response Rate**

Objective Response Rate (ORR) is defined as the number of randomized subjects who achieve a best response of complete response (CR) or partial response (PR) based on BICR assessments (using RECIST v1.1 criteria) divided by the number of randomized subjects. Best Overall Response (BOR) is defined as the best response, as determined by the BICR, recorded between the date of randomization and the date of objectively documented progression per RECIST v1.1 criteria or the date of subsequent therapy (including tumor-directed radiotherapy and tumor-directed surgery), whichever occurs first. For subjects without documented progression or subsequent therapy, all available response designations will contribute to the BOR determination. Confirmation of response is required at least 4 weeks after the initial response.

ORR will be summarized using a binomial response rate. The Clopper-Pearson method will be used to estimate the two-sided 95% confidence interval. BOR will be summarized by response category. Summary statistics of time to objective response will be provided for subjects who achieve a BOR of PR or CR, as assessed by the BICR.

Objective Response Rate as assessed by investigator will be summarized in the same manner as per BICR.

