#### **7.4.3.2 Subsequent Cancer Therapy**

Number and percentage of subjects receiving subsequent cancer therapies will be summarized. Categories include:

- Subsequent systemic therapy
- Subsequent surgery for treatment of tumors
- Subsequent radiotherapy for treatment of tumors

A by-subject listing of subsequent cancer therapy will also be produced for all randomized subjects.

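### Partial start dates of post-randomization radiotherapy and surgery are imputed to the earliest possible day with no check against progression, so a procedure that followed BICR progression can be dated before it

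*SAP*

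**What the plan says.** **Imputation.** SAP Section 8 sends partial radiotherapy and surgery dates to Appendix 2.
- Day missing: the procedures rule is to "impute as first day of that month and year", or to use the first-dose date if the month is that of first dose. Surgery rule B, which covers surgeries recorded outside the prior-surgery CRF page, does the same: "then impute as first day of that month and year".
- Day and month missing: surgery rule B reads "If both day and month are missing then impute as maximum between 01JAN of the year and date of the first dose", and the procedures rule is equivalent.
- No imputed start is compared with a progression or scan date. Only an imputed end date is checked, against death or last known alive.

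**Primary PFS.** Table 4.1.1.1-1 has a row for "Subsequent anti-cancer therapy started without death or progression per RECIST v1.1 reported prior or on the same day". Such a participant is censored at the last evaluable scan up to the therapy start, or at randomization if there is no on-study scan by then. Progression counts as an event only if no new therapy began before it. SAP 7.5.1 uses this definition for the primary log-rank test.

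**What counts as subsequent therapy.** SAP 4.1.3 ends the best-overall-response window at progression or subsequent therapy, "including tumor-directed radiotherapy and tumor-directed surgery". SAP 7.4.3.2 lists "Subsequent radiotherapy for treatment of tumors", with a matching surgery category. SAP 4.1.1.1 names neither procedure.

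**Expected order.** Protocol 7.7.2.1 permits palliative radiotherapy or surgery on condition that "The participant is considered to have progressed at the time of palliative therapy".

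**The concern.** An earliest-day rule looks cautious, but here it works on the order of two events. When progression and procedure fall in the same incompletely recorded period, it places the procedure first even if progression came first. A documented progression can then drop out of the primary analysis. Its replacement is informative censoring, because the participant leaves the risk set at or before a known failure.

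Section 8 bounds other imputed dates: partial death dates against last known alive, and partial progression dates against death. The procedure start is the date that can trigger censoring, and it has no such bound, which suggests an oversight.

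**Working it through.** **1. The plan's own figure.** Inputs from SAP 5 and 5.2: 365 events, HR 0.73, final alpha 0.049 two-sided. Power = Φ(√365/2 × |ln 0.73| − z) = Φ(9.552 × 0.3147 − 1.969) = Φ(1.037) = 85.0%, matching the stated 85%. It is used below only for scale.

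**2. One record through the rules.** Randomized 04FEB2019, first dose 05FEB2019, Week 12 scan 29APR, Week 20 scan 24JUN showing BICR progression, surgery 28JUN. Assume surgery counts as subsequent therapy for PFS.

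| Surgery date recorded as | Imputed start | Primary PFS outcome |
|---|---|---|
| 28JUN2019 | 28JUN2019 | Event, 24JUN2019 |
| JUN2019 | 01JUN2019 | Censored, 29APR2019 |
| 2019 | 05FEB2019 | Censored at randomization |

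**3. How often the order is reversed, given a partial date.** Assume the procedure follows progression by a fixed gap of g days and progression is spread evenly over the calendar. Progression on the imputed day itself is kept.
- Day missing: in a month of L days the event is lost when progression falls on day 2 to day L − g, that is on L − g − 1 days. For g = 14 the count over a year is 7×16 + 4×15 + 13 = 185, and 185/365 = 51%. For g = 3 it is 317/365 = 87%, and for g = 28 it is 18/365 = 5%. From g = 30 it is zero, so none is lost at 60 days or more.
- Day and month missing: the count is 364 − g days. For g = 14, 350/365 = 96%; for g = 90, 274/365 = 75%.

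A simulation on the SAP scan schedule, with the SAP 5.1 medians and cure fractions and randomization spread evenly over a year, gave the same shares. At g = 14, 18–20% of all day-missing records and 64–68% of year-only records ended as censoring at randomization. With a variable (exponential) gap averaging 14 days, the day-missing loss was 55%; with a mean of 60 or 90 days it was 20% or 14%.

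**4. Best overall response.** Scheduled scans up to Week 52 are at least 8 − 1 − 1 = 6 weeks (42 days) apart, later ones further, and no month exceeds 31 days. With only the day missing, the only scheduled scan lost is therefore the progression scan, and a documented response survives. With a year-only date, every scan after 1 January or first dose is lost, so a response followed by progression in the same year can disappear from ORR.

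**5. Total effect.** The documents do not give the number of partial dates. For illustration, assume 20–40% of the 365 events are followed by such a procedure and 1–5% of those dates are partial: 365 × 0.20 × 0.01 = 0.73 to 365 × 0.40 × 0.05 = 7.3 records. At g = 14:
- all day-missing: × 0.507 gives about 0.4 to 3.7 events;
- all year-only: × 0.959 gives about 0.7 to 7.0 events.

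If 7 events were lost and not replaced, power would be 84.3%. A loss of 37 (10% of 365) would give 81.1%.

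**The case against.** **Procedures do not always follow BICR progression.** A reader might infer from Protocol 7.7.2.1 that on-study radiotherapy and surgery come only after progression, so that the imputation always reverses the required order. The documents do not support that. Protocol 7.7.2.2 allows resection of solitary lesions after the Week 20 assessments without progression. Progression in 7.7.2.1 is linked to Protocol 8.1.2.2, where the investigator assesses it, while primary PFS uses BICR. A procedure can properly precede BICR progression, and censoring is then what the table intends. This stands: the shares in step 3 apply only where BICR progression truly came first.

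**The PFS link is inferred.** SAP 4.1.1.1 does not name the procedures. SAP 7.2.1 describes on-study anti-cancer therapy without mentioning either, and Protocol 7.7.1.1 includes only extensive, non-palliative radiation among prohibited anti-neoplastic therapy. This also stands. For best overall response the link is explicit.

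**There are safeguards.** The secondary (ITT) PFS definition ignores subsequent therapy. SAP 7.5.2 plans sensitivity analyses under both definitions and a by-subject listing of censoring and reason under each. Affected participants should be traceable, but the primary test still uses the exposed definition.

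**The effect may be trivial.** The final PFS analysis is triggered by events, so lost events mainly delay it. The trial is double-blind, and nothing in the documents shows a difference between arms.

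**Conclusion.** The defect is real but conditional. Appendix 2 can date a procedure before a BICR progression that truly preceded it when both fall in the same recorded month (day missing) or year (day and month missing). Best overall response then loses scans. Primary PFS loses the event only if tumor-directed radiotherapy and surgery count as subsequent anti-cancer therapy there, which the SAP implies without stating.

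At a 14-day gap, about half of day-missing and about 96% of year-only records would be affected; at 60 days or more with the day missing, none. These shares assume the order progression then procedure. The overall size is unknown and probably small: the range of about 0.4 to 7 events rests on assumed rates. A reader might go further and conclude that the reported PFS result is biased or underpowered; nothing in the documents shows that.

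**What to change.** 1. State in SAP 4.1.1.1 whether tumor-directed radiotherapy and surgery trigger PFS censoring.
2. Add to Appendix 2: if the partial period contains a documented BICR progression, impute the procedure start no earlier than the day after that progression.
3. List every participant with a partially dated post-randomization procedure and report results under the current and the amended rule. If the list is empty, the question closes.

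SAP 5.2.1 records that primary PFS was tested on 09MAR2021 and led to unblinding at subject level. For PFS the amended rule should therefore be a labelled sensitivity analysis that does not replace the result. For ORR, which the same section says had not been analysed or summarized by arm, it can be prespecified, with the date of the decision recorded.

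A floor at the day after the last study dose is not a sound alternative. Protocol 7.7.2.1 foresees dosing resuming after palliative radiotherapy, so that floor would misdate on-treatment procedures.

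The cost is a few sentences and a small programming change, with no new data. The drawback is that the rule assumes progression came first when the date cannot settle it. That may be wrong for procedures prompted by investigator-assessed progression or for resections under Protocol 7.7.2.2, and reporting both rules covers this.
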